9.0 CRITERIA FOR INTERVENTION DISCONTINUATION

These include:

- Patient's consent withdrawn
- Patient's discharge from the ICU
- Allergy to any of the components of EMR
- Patient requiring renal replacement therapy
- Patient's death
- Patient changed to Comfort Care status
- Patients receiving greater than 70% of their nutritional needs via enteral nutrition
- Unable to undergo placement of CVC for any technical reasons or withdrawal of CVC
- Severe fluid overload or electrolyte abnormality requiring discontinuation (as described in Chapter 7)
- Jehovah's Witness who decides not to accept albumin.
- If patient develops a known contraindication, or an unspecified condition where the clinician thinks the patient should be taken off the protocol, then there should be a discussion and treatment should be weaned according to safety protocol.

In case of discontinuation, please follow weaning procedure detailed in section 6.7.

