5.2 Exclusion Criteria

- Do Not Resuscitate (DNR),
- Comfort Care and end-of-life patients
- Patients with SOFA score greater than 12
- Pregnant women
- Jehovah witnesses that do not accept albumin.
- Active bleeding (e.g., gastrointestinal bleeding)
- Acute neurological syndromes (e.g., stroke, hemorrhage, etc)
- End-stage Renal Disease (ESRD)
- Transaminitis

- Renal replacement therapy
- Chronic Liver Disease
 - Childs-Pugh Class C or
 - Diagnosis of Cirrhosis
- Heart rate less than 50 bpm,
- Respiratory rate less than 8 rpm,
- Temperature less than 95°F or 35°C
- Tumor Lysis Syndrome
- Myasthenia gravis
- Sulfite Allergy: amino acids administration are contraindicated. It is more common in steroid dependent asthmatics. (Please note that this is NOT sulfa allergy and is NOT contraindicated patients with sulfa allergy). Sulfites are present in dried fruits, beer, wines, sausages, jams, maple syrup, and many other food products.
- Serum sodium concentration < 130 mEq/L or >150 mEq/L (Note: Once serum sodium levels are \geq 130 or \leq 150 mEq/L within 12 hours after meeting inclusion criteria, the patient can then be considered for the study. This is only a temporary restriction).
- Serum Creatinine level: SCr \geq 3 mg/dL (Note: Once serum creatinine levels are \leq 2.5 mg/dL within 12 hours after meeting inclusion criteria, the patient can then be considered for the study. This is only a temporary restriction).
- Urine output < 400 cc/24hrs (Note: Once urine output levels are \geq 400 cc within 12 hours after meeting inclusion criteria, the patient can then be considered for the study. This is only a temporary restriction).
- Hyperkalemia K > 5.5 mEq/L (Note: Once potassium levels are \leq 5.5 mEq/L within 12 hours after meeting inclusion criteria, the patient can then be considered for the study. This is only a temporary restriction).
- Hyperglycemia: Glucose > 250 mg/dL (Note: Once glucose is below 250 mg/dL within 12 hours after meeting inclusion criteria, the patient can then be considered for the study. This is only a temporary restriction.)

- Hypophosphatemia: Serum Phosphorous < 1.5 mg/dL (Note: Once phosphorus is above 1.5 mg/dL within 12 hours after meeting inclusion criteria, the patient can then be considered for the study. This is only a temporary restriction.)

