6.2 Description of EMR protocol group

The combined EMR solution will be infused at a set rate (<12hours or > 12 hours) as the main metabolic resuscitation strategy. Additional volume may be required to achieve euvoolemia. This will be in the form of either albumin (if serum albumin < 3 as mentioned below) or crystalloids depending on the clinical situation and the serum sodium content.

The early metabolic support components include the following:

Table 2 show the components of the EMR solutions per liter

Table 2. EMR Solution

EMR SOLUTION WILL BE PREPARED IN A BAG WITH THE FOLLOWING COMPONENTS	
EMR I (with potassium)	EMR II * (without potassium)
Dextrose 50% with Potassium Phosphate 30 mmol	Dextrose 50% with Sodium Phosphate 30 mmol
Sodium Acetate 75 mEq	Sodium Acetate 55 mEq
Sodium Chloride 75 mEq	Sodium Chloride 55 mEq
Thiamine 500 mg	Thiamine 500 mg
Folic Acid 1 mg	Folic Acid 1 mg
Zinc Sulfate 5 mg	Zinc Sulfate 5 mg
Selenium 60 mcg	Selenium 60 mcg
Copper 1.2 mg	Copper 1.2 mg
Chromium 12 mcg	Chromium 12 mcg
Magnesium Sulfate 16 mEq	Magnesium Sulfate 16 mEq
Multivitamin for Injection 10 ml	Multivitamin for Injection 10 ml

Insulin 25 units (actrapid)	Insulin 25 units (actrapid)
SPECIFICATIONS OF THE TREATMENT AND ADJUVANTS	

A. EMR solutions: will be infused at 0.5 ml/kg/h by CVC. If serum glucose is greater than 180mg/dL-250mg/dL, EMR solution will be infused at 0.25 ml/kg/h. Prior to starting EMR infusion, a bolus of 500mg IV of thiamine should be administered to all patients on SC+EMR arm of treatment.
 
B. Clinisol 15% AA. Infusion rate (IV) will be 0.25 ml/kg/hr for the first 12 hours, then 0.5 ml/kg/h for the remainder of the intervention – this must be infused via a dedicated Central Venous Catheter.
 
C. If serum albumin is lower than 3 g/dL, then use Albumin 25% 100ml IV Q 8 hours until serum albumin level \geq 3 g/dL – this can be infused peripherally or centrally. Once albumin >3g/dL this can be stopped, but should resume whenever albumin falls <3g/dL
 
D. Vitamin C 1g q 8h IV (100 ml per gram of Vitamin C)
	

**If the level of K is \geq 5.0mmol/L the patient will receive EMR II. Any conditions, which the K⁺ trend is rising, clinicians could opt to switch EMR solution to prevent hyperkalemia.*

This solution does not contain potassium phosphate, but contains sodium phosphate. Sodium content is consequently adjusted to have a compatible concentration

Total amount of administered fluids on day one.

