6.7 Weaning procedure for EMR solution

To wean EMR, decrease rate of both solutions, EMR I or II and Clinisol to half the current rate for 4 hours, and then discontinue. Check serum glucose within 30 minutes of discontinuation of EMR. Further decisions regarding management of IVF, amino acid infusions or parenteral nutrition will be at the discretion of the ICU team or the primary team.

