- i. Study intervention is to be stopped. Record as adverse event. Manage as per ICU protocol

f. Hypomagnesemia (Mg <1.5mg/dl)

- i. Replace as per ICU guidelines – N.B. target magnesium is ≥ 3 mg/dl in intervention group

g. Aluminum toxicity

- i. Aluminum toxicity is seen in neonates; however, this population is excluded in our study.

- ii. Patients in renal failure are at risk of bio-accumulating aluminum when solutions contain >50 micrograms/L. In this study, patients with renal failure are excluded and free amino acids only contains <25 micrograms/L.
- iii. Currently, to measure blood aluminum levels is not standard of care in a) patients not at risk of bio-cumulating the metal, b) patients receiving solutions that contain aluminum below 50 micrograms/L.
- iv. Aluminum toxicity is not an expected adverse event in this study patient population.

h. Hypophosphatemia (PO4 <1mg/dl)

- i. Additional replacement as per standard ICU guidelines

i. Hyperphosphatemia (PO4 >6.5mg/dL)

- i. Check renal function and calcium. Discuss with principal investigator. Hyperphosphatemia is not usually symptomatic and does not usually cause direct toxicity. The product of calcium x phosphate should be less or equal to 60. Record as adverse event

3. Hyper/hypoglycemia (see appendix)

For the very likely event of hyper/hypoglycemia in the EMR group we have developed an algorithm, which is a slight modification of standard ICU glucose management protocols and itself refers to ICU sliding scale insulin protocols. As glucose management is anticipated as a potential issue, monitoring of glucose is to occur at least hourly in the treatment arm. Please see appendix for detailed information on glucose management. Target glucose is 140-180mg/dl.

4. Allergic reactions (related to study components or suspected relation)

- Urticarial reaction
 - Begin antihistamine. Record as possible adverse event. Monitor patient – if EMR components suspected as the causative AND worsening reaction consider stopping solution and replace with D50 IV solution and exclude the patient from the protocol. At the same time treat the patient until reaction resolves. (Frequent glucose monitoring once solution discontinued). Contact principal investigator and follow hypersensitivity institutional protocol.
- Anaphylaxis

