 - As mentioned above, if EMR causes an anaphylaxis reaction, begin emergency anaphylaxis management as per ICU protocol. Record serious adverse event and inform research team immediately. Stop solution and replace by D50 IV solution until a decision is made to exclude the patient from the protocol. At the same time treat the patient until reaction resolves. Caution with glucose once EMR is stopped – glucose management algorithm must continue to be followed. Contact study lead.

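### Section 9.0 sends every discontinuation through the four-hour wean and makes no exception for the events where Section 8.2 says to stop

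*Combined protocol and SAP*

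**What the plan says.** Section 9.0 (Criteria for Intervention Discontinuation) is a single list. It includes "Allergy to any of the components of EMR", with no limit on severity, and severe fluid overload or an electrolyte abnormality that requires discontinuation. Its last line applies to the whole list: "In case of discontinuation, please follow weaning procedure detailed in section 6.7".

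Section 6.7 defines the wean: "decrease rate of both solutions, EMR I or II and Clinisol to half the current rate for 4 hours, and then discontinue". Serum glucose is then checked within 30 minutes.

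Section 8.2 handles the same events differently:

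- **Anaphylaxis caused by EMR:** start emergency management under the ICU protocol, and "Stop solution and replace by D50 IV solution until a decision is made to exclude the patient from the protocol".
- **Urticarial reaction with EMR suspected:** "AND worsening reaction consider stopping solution and replace with D50 IV solution and exclude the patient from the protocol". This is discretionary.
- **Severe hypermagnesemia (Mg above 4 mg/dl):** the study intervention is to be stopped and the patient managed under the ICU protocol. No wean is mentioned.

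For severe fluid overload, hypernatremia, and hyponatremia with suspected SIADH, Section 8.2 does speak of weaning.

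**The concern.** Within 8.2, some events lead to a wean and others to a stop. The closing line of 9.0 removes that difference and prescribes the wean for all of them. A member of staff who reaches 9.0 by way of the allergy item finds no pointer to 8.2. The one cross-reference in the list to adverse event management goes to Chapter 7, which is Study Procedures.

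What is at stake is a bedside instruction. Taken at its word, 9.0 asks for four more hours of a suspected allergen at half rate, or of a bag containing magnesium in a patient whose magnesium is already too high. The wean names Clinisol, the amino acid solution, and the protocol itself recognises an allergy that bars it (Section 5.2: "Sulfite Allergy: amino acids administration are contraindicated"). Known sulfite allergy is excluded at entry, so this matters only for an allergy first recognised during the infusion.

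**Working it through.** **The texts side by side**

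| Event | Section 8.2 | Section 9.0 with 6.7 |
|---|---|---|
| Anaphylaxis due to EMR | Stop, replace with D50 | Half rate for 4 h, then off |
| Worsening urticarial reaction, EMR suspected | Consider stopping, replace with D50 | Half rate for 4 h, then off |
| Severe hypermagnesemia | Stop | Half rate for 4 h, then off |
| Severe fluid overload, where slowing the study solution is felt essential | Wean | Half rate for 4 h, then off |

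The two columns agree only in the last row. No sentence in 6.7, 8.2 or 9.0 says which section prevails.

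**Inputs for the volume (Section 6.2)**

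- EMR rate: 0.5 ml/kg/h, or the lower rate: "If serum glucose is greater than 180mg/dL-250mg/dL, EMR solution will be infused at 0.25 ml/kg/h".
- Clinisol 15% rate: "0.25 ml/kg/hr for the first 12 hours, then 0.5 ml/kg/h for the remainder of the intervention".
- Weight: 70 kg, the protocol's own example.

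**Check against the plan's figures.** Volume = rate × weight × time. First 12 hours: (0.5 + 0.25) × 70 × 12 = 630 mL. After 12 hours: (0.5 + 0.5) × 70 × 12 = 840 mL. Both match Section 6.2.

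**Volume of a literal wean.** For each solution, (rate ÷ 2) × weight × 4 h = 2 h × rate × weight. A full wean therefore gives as much as two hours at the rate in force when it begins.

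| EMR rate (ml/kg/h) | Clinisol rate (ml/kg/h) | EMR (mL) | Clinisol (mL) | Total at 70 kg (mL) |
|---|---|---|---|---|
| 0.25 | 0.25 | 35 | 35 | 70 |
| 0.25 | 0.5 | 35 | 70 | 105 |
| 0.5 | 0.25 | 70 | 35 | 105 |
| 0.5 | 0.5 | 70 | 70 | 140 |

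Per kilogram this is 2 × 0.5 = 1 mL to 2 × 1.0 = 2 mL.

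**What the volume contains.** Clinisol at 15%: 35 × 0.15 = 5.25 g to 70 × 0.15 = 10.5 g of amino acids. Magnesium sulfate in EMR is 16 mEq per litre (Table 2 in Section 6.2): 0.035 × 16 = 0.56 mEq to 0.070 × 16 = 1.12 mEq.

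**If 8.2 is applied first.** With both infusions already off, the current rate is 0 and the wean adds 0 mL. If the word solution in 8.2 were taken to mean EMR I/II alone, the Clinisol share of 35 to 70 mL would remain.

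**The case against.** The strongest reply is that the hazard is already handled. Section 8.2 is the specific emergency rule and invokes ICU anaphylaxis management and, for urticarial reactions, the institutional hypersensitivity protocol. Section 8.1 lets the care team discontinue at its discretion. The anaphylaxis text has staff stop and give D50 while exclusion is decided, so formal discontinuation under 9.0 can come after the stop, when nothing is left to wean. The 9.0 list also includes death and loss of the central line, where a four-hour wean is meaningless or impracticable. Its last line is therefore best read as a default for non-emergency stops.

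Most of this stands, and it keeps the practical risk low. It does not put an exception into the text. A reader has to supply the order of precedence.

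Two further limits are fair. For urticaria, 8.2 only offers stopping as an option, so there is no firm clash. For hypermagnesemia, 8.2 says stopped but not at once, and Section 6.3 uses the same word for an ending that includes a wean. That case is less firm than anaphylaxis, although 8.2 names weaning for other electrolyte events and not for this one.

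A reader might infer that the protocol orders staff to keep infusing through anaphylaxis, or that patients would be harmed. The documents do not support either. Section 8.2 says the opposite for anaphylaxis, the sections can be followed in sequence, and no event frequency is given. Nor is it clear that Clinisol would be left running: 6.2 lists it among the early metabolic support components, and the allergy heading in 8.2 covers study components generally.

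**Conclusion.** Wrong as written, and minor. The closing line of 9.0 is too general: it applies the wean to allergy and electrolyte discontinuations without excepting those that 8.2 says to stop (anaphylaxis, severe hypermagnesemia) or lets staff stop (a worsening urticarial reaction suspected to be due to EMR).

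The exposure at issue is bounded by the working: nothing if 8.2 comes first and covers both infusions, and at most 2 mL/kg if 8.2 is bypassed. The upper figure assumes that the full four hours are completed with no further rate change. These are volumes, not estimates of harm.

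No endpoint, population, sample size, error rate or analysis depends on the point.

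**What to change.** Replace the last sentence of Section 9.0 with:

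> Follow the weaning procedure in section 6.7, except where section 8.2 calls for stopping (anaphylaxis, a worsening allergic reaction where the decision is to stop, severe hypermagnesemia): stop EMR I/II and Clinisol at once, give D50 for allergic reactions as in 8.2, and continue the glucose algorithm.

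This keeps the purpose of the wean, which Section 6.3 gives as avoiding hypoglycemia. The 30-minute glucose check in 6.7 should still apply after an abrupt stop, above all in hypermagnesemia, where 8.2 does not provide D50. In the same amendment, correct the Chapter 7 reference in the 9.0 list to Section 8.2.

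The cost is one sentence and one cross-reference, with IRB review of the amendment (Section 12.1). Staff training is given before the study begins (Section 11.4.1), so a later change also needs a short notice to ICU staff. It adds no visits, tests or patients.

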10.0 STATISTICAL CONSIDERATIONS

10.1 Study Endpoint and Outcomes

The primary objective of this study is to assess the efficacy of administering Early Metabolic Resuscitation with Standard of Care (SC + EMR) in patients diagnosed with septic shock for reducing 28 day mortality versus using the Standard of Care alone (SC).

The primary endpoint of the study is 28-day mortality. The rationale for selecting the 28-day timeframe as the primary endpoint for comparison is that the MDACC ICU length of stay and the hospital length of stay in patients diagnosed with septic shock have wide variability (ICU LOS = Mean 9.45 ± 13.06 min: 0 max: 104, and Hospital LOS = Mean $26.4 \pm SD 26.4$ min:1, max: 242). This variability is incurred from sources that cannot be controlled. For this reason, measures such as 28-day and 90-day mortality provide more objectivity and align with outcomes described in the literature.

Secondary outcomes include ICU mortality, hospital mortality, 90-day mortality, incidence of acute kidney injury (dichotomous variable), time on cardiovascular support (continuous variable), time on ventilator (continuous variable) and length of ICU and hospital stays (continuous variables).

10.2 Sample Size Justification and Randomization

The rate of 28 day mortality from septic shock at the UT MD Anderson Cancer Center was 70% in 2017. With the objective of decreasing this rate to 40%, a sample size of 112 patients (56 per group) provides 90% power to detect a 30% absolute reduction in the rate of 28 day mortality using a two-sided chi-square test at the 0.05 significance level. We plan to use stratified randomization in a 1:1 fashion to assign patients into two groups, and a fixed block size consisting of 4 patients will be applied for this purpose. The randomization will be conducted in CORe (Figure 2).

Tables 3 displays effect sizes that correspond with conducting a test of equal proportions after randomizing 56 patients to each study arm. The first scenario in Table 3 is what we have currently provided in the protocol. Subsequent scenarios in Table 3 illustrate the change the in the effect size as the Type I error increases. Table 4 is provided to illustrate effect size results if the power is reduced to 80%. Smaller effect sizes are detectable if you increase Type I error or reduce power.

Table 3. Effect size with varying Type I error with Sample Size and Power controlled at 56 patients per study arm and 90%, respectively

Sample Size Per Study Group	Effect Size (percentage point change from $\hat{\pi}_0 = 70\%$)	Type I error
N = 56	-30% (0.70 vs 0.40)	0.05
N = 56	-27% (0.70 vs 0.43)	0.10
N = 56	-25% (0.70 vs 0.45)	0.15
N = 56	-24% (0.70 vs 0.46)	0.20

[figure not shown]
Estimates provided by (nQuery Advisor v7.0) for the difference between two proportions using a two-sided chi-square test.

Table 4. Effect size with varying Type I error with Sample Size and Power controlled at 56 patients per study arm and 80%, respectively

Sample Size Per Study Group	Effect Size (percentage point change from $\hat{\pi}_0 = 70\%$)	Type I error
N = 56	-26% (0.70 vs 0.44)	0.05
N = 56	-23% (0.70 vs 0.47)	0.10
N = 56	-21% (0.70 vs 0.49)	0.15
N = 56	-20% (0.70 vs 0.50)	0.20

Estimates provided by (nQuery Advisor v7.0) for the difference between two proportions using a two-sided chi-square test

Figure 2. Sample size and randomization

[figure not shown]

The septic shock patients will be stratified by type of malignancy given that hematologic patients may be more morbid than solid tumor patients. SC + EMR: Early Metabolic Resuscitation plus Standard of Care SC: Standard of Care. Blue boxes represent the group of patients that will receive EMR plus Standard of Care intervention and the pink boxes represent the group that will receive Standard of Care alone.

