2.2 Epidemiology

Worldwide, 19 million cases of sepsis are calculated each year, however, it is presumed that this value may be even higher due to under reporting, which is considered high in low- and middle-income countries (3,4). According to the report of the Center for Disease Control and Prevention (CDC) of 2017, sepsis annually affects 1.5 million individuals in the United States, of whom 250,000 die (5), which includes it among the top 10 causes of death in the US. This generates annual costs of over 24 billion dollars(6); which makes this condition a public health priority.

In a recent study not yet published performed by [name] et al. in 2017, a sample of 305 patients (154 with hematologic malignancies and 108 with solid tumors) with the diagnosis of septic shock hospitalized in the ICU of The University of Texas MD Anderson Cancer Center were assessed. It was found that the 28 day mortality was 70%. These values shed light on the emergent requirement of seeking treatment alternatives that may improve outcomes in these patients.

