6.4 Adherence Assessment

Adherence will be defined as continuous infusion of study solutions 90% of the time from onset of study until cessation. This will be assessed via the electronic patient record, which will record infusion stop/start times.

Patients who have requested to be withdrawn from the study or achieve Comfort Care status during ICU stay will be removed from the study. Those who die or begin renal replacement will be followed up but the interventions will be stopped.

[figure not shown]

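### The 90% power is correct for 70% versus 40% with 56 analysed per arm, but neither the 70% control rate nor full analysis of 112 patients is shown to fit this trial

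*Combined protocol and SAP*

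**What the plan says.** Section 10.2, repeated in the Summary Table, takes its control rate from the centre's own experience: "The rate of 28 day mortality from septic shock at the UT MD Anderson Cancer Center was 70% in 2017". It continues: "With the objective of decreasing this rate to 40%, a sample size of 112 patients (56 per group) provides 90% power to detect a" 30-point absolute reduction, "using a two-sided chi-square test at the 0.05 significance level", with 1:1 allocation.

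The only source described for the 70% is in 2.2: an unpublished 2017 study of 305 patients with septic shock in the centre's ICU. Of these it says "It was found that the 28 day mortality was 70" per cent. No eligibility rule for that series is given.

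The trial population is narrower. Section 5.1 requires a total SOFA of at most 12, and 5.2 lists "Patients with SOFA score greater than 12" again as an exclusion. Section 5.2 also excludes DNR, comfort-care and end-of-life patients, renal replacement therapy, end-stage renal disease and cirrhosis, among others. Section 5.1 admits a lactate above 1 mmol/L, whereas 2.5 describes septic shock with a lactate above 2 mmol/L.

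On patients lost after randomisation, 6.4 states: "Patients who have requested to be withdrawn from the study or achieve Comfort Care status during ICU stay will be removed from the study". Section 8.2 also withdraws patients when severe fluid overload leads the primary team to stop the solution. Yet 7.2 says all patients are followed for up to 90 days, and 10.3 treats all 112 as the full analysis set.

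Tables 3 and 4 of 10.2 hold the control rate at 70% in all eight rows and vary the type I error and the power: "Subsequent scenarios in Table 3 illustrate the change the in the effect size as the Type I error increases".

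**The concern.** A power statement is only as good as its control rate and its analysed number. Here the control rate comes from a series that is not shown to have passed the trial's entry criteria. Several of those criteria remove patients who would be expected to have a high risk of death. The 40% target is presented as an objective, without effect data, so nothing in the plan says whether the absolute or the relative effect should carry over to a population at different risk. The number analysed is also uncertain, because 6.4 takes some patients out and the plan does not say how they count in the primary endpoint.

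The stake is interpretation. A null result will be read against a stated 90% power. If the power for the effect considered plausible was lower, that reading would be too strong.

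**Working it through.** **Inputs from 10.2.** Control 0.70, SC + EMR 0.40, n = 56 per arm, two-sided alpha 0.05, chi-square test, 1:1 allocation.

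**Formula.** With d = p1 − p2 and p̄ = (p1 + p2)/2,

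power = Φ{ [d√n − 1.960 √(2p̄(1 − p̄))] / √(p1(1 − p1) + p2(1 − p2)) }.

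**1. The plan's own figure.**
- d√n = 0.30 × √56 = 2.245.
- The null term is 1.960 × √(2 × 0.55 × 0.45) = 1.379.
- The denominator is √(0.21 + 0.24) = 0.671.
- Power = Φ[(2.245 − 1.379)/0.671] = Φ(1.291) = 0.902. The 90% reproduces.
- Solving for n at 90% power: (1.379 + 1.282 × 0.671)²/0.30² = 55.7, so 56. That is exactly the planned number, with nothing added for loss.

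The rows of Tables 3 and 4 of 10.2 also reproduce.

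**2. A plausible range for the eligible control rate.** This is an assumption, as the documents do not give the rate. If a fraction f of the series would be ineligible and a fraction m of those died, the eligible rate is (0.70 − f·m)/(1 − f):
- f = 0.2, m = 0.8: 0.54/0.80 = 0.675
- f = 0.3, m = 0.9: 0.43/0.70 = 0.614
- f = 0.4, m = 0.9: 0.34/0.60 = 0.567

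Reaching 50% would need, for example, 40% ineligible with every one of them dying: (0.70 − 0.40)/0.60 = 0.50. I therefore use 55% to 65%.

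**3. Power at 56 per arm over that range**, on three effect scales that all agree at 70% versus 40%. The relative risk is 0.40/0.70 = 0.571 (a 43% reduction). The odds ratio is (0.40/0.60)/(0.70/0.30) = 0.286.

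| Control rate | Same relative risk | Same odds ratio | Same 30 points |
|---|---|---|---|
| 70% | 0.902 (vs 40.0%) | 0.902 (vs 40.0%) | 0.902 (vs 40%) |
| 65% | 0.848 (vs 37.1%) | 0.905 (vs 34.7%) | 0.899 (vs 35%) |
| 60% | 0.786 (vs 34.3%) | 0.902 (vs 30.0%) | 0.902 (vs 30%) |
| 55% | 0.717 (vs 31.4%) | 0.892 (vs 25.9%) | 0.911 (vs 25%) |

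The last two columns keep their power by assuming a larger relative effect. At 60%, a 30-point drop is 30/60 = 50%; at 55% it is 30/55 = 55%.

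**4. Removals**, if removed patients leave the primary analysis (70% versus 40%; rates assumed):
- 10% per arm, unrelated to outcome (n = 50.4): 0.868. At 20% (n = 44.8): 0.826.
- 20% of the deaths in each arm removed: 48.2 and 51.5 patients remain, with mortality 0.56/0.86 = 0.651 and 0.32/0.92 = 0.348. Power is 0.869.
- 10% of each arm removed, all of them deaths: mortality 0.60/0.90 = 0.667 and 0.30/0.90 = 0.333. Power rises to 0.929.

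**5. Both together.** A 60% control rate, the same relative risk and 10% random removal give 0.741.

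**The case against.** The strongest reply is that 10.2 claims power for a 30-point absolute reduction, and that claim is correct. It is also robust: if 30 points is the effect, a control rate of 55% to 65% leaves power at 0.90 to 0.91. That stands, and the same is nearly true for a constant odds ratio. The loss appears only if the relative reduction is what carries over. The plan never states a relative effect, but it gives no evidence that the absolute difference would persist in a lower-risk population either.

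A reader might infer that the source series was unselected. Section 2.2 only fails to describe selection, and the sponsor can settle this by stating the rules. A reader might also infer that every entry criterion lowers mortality. No document gives mortality by criterion, and some criteria may act the other way: the vasopressor requirement, cardiovascular SOFA of at least 2, and failure to tolerate adequate enteral nutrition. A net downward shift is plausible, but its size is unknown.

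On removals, 6.4 does not say that removed patients leave the primary analysis, and 7.2 and 10.3 point the other way. Moves to comfort care are likely to be tied to death, so removing them need not lower nominal power. The more serious consequence would be bias from outcome-related exclusion in an unblinded trial.

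Tables 3 and 4 of 10.2 are correct for what they set out to show. Replacing their rows would be a matter of preference.

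**Conclusion.** The point holds as one of justification, not of calculation. The 90% is right for 70% versus 40% with 56 analysed per arm. The plan does not show that 70% applies to patients meeting 5.1 and 5.2, makes no allowance for loss, and shows no sensitivity to the control rate.

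For an assumed eligible rate of 55% to 65% and no loss, power is 0.72 to 0.85 under the planned 43% relative reduction, and 0.89 to 0.91 under a constant odds ratio or 30-point difference. Random removal of 10% at the planned rates gives 0.87.

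It is tempting to conclude that the trial is underpowered, perhaps near 50% or 65%. The documents do not support that. Those figures need control rates of 40% or 50% together with a constant relative risk, and nothing in the plan points to rates that low.

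**What to change.** 1. Apply 5.1 and 5.2 to the 305-patient series, as far as its data allow, and report 28-day mortality in those who qualify. State any selection already applied to the series.
2. Restate the power in 10.2 and the Summary Table at that rate, giving both the absolute and the relative effect assumed and the number expected to be analysed.
3. Add control-rate rows to Tables 3 and 4 of 10.2, keeping the existing rows.
4. State that all randomised patients count in the 28-day mortality analysis, and reconcile 6.4 with the follow-up statement in 7.2 and the full analysis set in 10.3. If some loss is unavoidable, such as withdrawn consent with unknown vital status, give its expected size.

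The cost is a re-analysis of an existing series and some revised text. No change in sample size is required. The downside for the sponsor is that the stated power may become less favourable.
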